1.0 TRIAL SUMMARY

[figure not shown]
Abbreviated Title	Neoadjuvant pembrolizumab for resectable early stage gastroesophageal adenocarcinoma
Trial Phase	IIa
Clinical Indication	Resectable cT1b-2N0M0 gastroesophageal adenocarcinoma
Trial Type	Prospective clinical trial
Type of control	Historical controls
Route of administration	Intravenous
Trial Blinding	None
Treatment Groups	1
Number of trial participants	33
Estimated enrollment period	24 months
Estimated duration of trial	36 months
Duration of Participation	Until 5 years post-surgical resection, death, or study closure
Estimated average length of treatment per patient	8-11 weeks (pembrolizumab IV q 3 weeks x 3 cycles followed by surgery within 8-11 weeks from first dose of pembrolizumab)

2.0 TRIAL DESIGN

2.1 Trial Design

This is a prospective, single-arm phase IIa study enrolling patients with cT1b-2N0Mx esophageal and gastric adenocarcinoma. Patients will receive 3 cycles of pembrolizumab 200mg intravenously on day 1 of a 3-week cycle. After 3 cycles, patients will undergo surgery. The target surgery date is 8-11 weeks after the first dose of pembrolizumab. Surgical approach will vary based upon tumor location but would entail tumor resection with either D2 or two-field lymphadenectomy. The primary objective is to determine the pathologic complete response (pCR) rate in patients with cT1b-T2N0 gastroesophageal adenocarcinoma (GEA) treated with neoadjuvant pembrolizumab followed by surgical resection. A sample size of 33 patients will provide 90% power with one-sided alpha 0.1 to detect a pCR rate of 15% using neoadjuvant pembrolizumab. Secondary endpoints include R0 resection rate, safety and tolerability, disease-free survival (DFS), and overall survival (OS). Diagnostic tissue biopsy and surgical resection specimen pre- and post-pembrolizumab therapy will be assessed for panel DNA/RNA next generation sequencing (NGS), programmed death-ligand 1 (PD-L1) combined positive score (CPS) testing, Epstein-Barr virus (EBV) testing, microsatellite instability (MSI) testing and tumor mutation burden (TMB). Plasma circulating tumor DNA (ctDNA) samples will be collected for panel NGS (73 gene in real time, and more stored for larger 550 gene and smaller higher depth panels) prior to pembrolizumab therapy, after neoadjuvant pembrolizumab therapy but prior to surgery, after surgery, and upon recurrence if/when this occurs. Stool samples will also be obtained at these time points and subjected to Fecal 16S RNA seq.

2.2 Trial Diagram

3.0 OBJECTIVES & HYPOTHESES

3.1 Primary Objective & Hypothesis

Objective:

To determine the pathologic complete response (pCR) rate in patients with cT1b-T2N0 GEA treated with neoadjuvant pembrolizumab followed by surgical resection.

Regression of the primary tumor will be documented by the amount of viable tumor versus the amount of fibrosis (Becker Criteria), ranging from no evidence of any treatment effect to a complete response with no viable tumor identified, as previously described[1] [Grade 1a: complete remission (pCR), no residual tumor/tumor bed; Grade 1b: subtotal remission, <10% residual tumor/tumor bed; Grade 2: partial remission, 10-50% residual tumor/tumor bed; Grade 3: minor/no remission, >50% residual tumor/tumor bed].

Hypothesis:

The pCR rate (Grade 1a+b response) in patients with cT1b-T2N0 GEA who receive neoadjuvant pembrolizumab followed by surgical resection will be 15%, whereas historical patients treated with surgery alone have a pCR rate of virtually 0%. [2, 3]

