4.2 Rationale

4.2.1 Rationale for the Trial and Selected Population

Gastroesophageal cancer is the second leading cause of cancer mortality worldwide. [20] Surgery and endoscopic resection are the only curative options for patients with early stage and/or locally advanced operable GEA. Survival is highly dependent on the extent of disease at presentation, in particular the depth of invasion and nodal status, as well as ability to obtain a complete (R0) resection and pCR. [21] The role of perioperative chemotherapy is clear in \geq cT3 and/or \geq cN1 disease where R0 resection rates are 80-90% and pCR 15-25%. However, the benefit of such therapy in cT2N0 disease is less certain, and in cT1bN0 disease even less well studied. This is in part due to significant heterogeneity that exists in the enrollment criteria for the major clinical trials that have guided the use of neoadjuvant therapy. Trials have varied in their inclusion of cT2N0 disease, use of EUS for staging, use of AJCC staging system, and reporting of outcomes by T and N status. There is thus great heterogeneity across treatment centers regarding the inclusion of cT1b-2N0 patients in perioperative therapy approaches. A recent retrospective analysis of 1704 patients with cT2N0 gastric cancer found that there was no overall survival benefit derived from neoadjuvant and/or perioperative chemotherapy compared to surgery alone.[22]

However, patients with cT2N0 esophageal adenocarcinoma (AC) (clinical stage IIB based on the AJCC 8th edition) have a 5-year risk-adjusted survival of only ~42% [23], a dismal number, and actually comparable to patients with stage III colon cancer where routine adjuvant therapy is implemented. Patients with cT1N0 esophageal AC (clinical stage I), have a 5-year risk-adjusted survival of only approximately 68%. Patients with cT1-2N0M0 gastric AC (clinical stage I) have an estimated 5-year survival of 57%. [24] There is a clear need to improve on outcomes in patients with operable GEA. It is quite evident that the optimal treatment of cT1-2N0 GEA is controversial without widespread implementation of any perioperative therapy, yet with acknowledged relatively poor outcomes. At the University of Chicago and many other centers, the standard of care for cT1-2N0 GEA is surgical or (endoscopic mucosal resection/dissection if early stage I cT1a) followed by observation.

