4.2.3 Rationale for Endpoints

4.2.3.1 Efficacy Endpoints

There is compelling evidence that pathologic complete response rate is an early surrogate endpoint for survival in GEA. In patients with gastric cancer treated with neoadjuvant platinum-based chemotherapy, complete or subtotal tumor regression has been shown to be a prognostic factor independent from ypT and ypN stage.[28] In a large meta-analysis of patients with resectable GEA treated with neoadjuvant chemotherapy followed by surgery, those who achieved a pCR had improved survival than patients who did not achieve a pCR.[29] Thus, histopathologic regression measured as pCR rate is an appropriate endpoint for this phase 2 trial.

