9.0 STATISTICAL ANALYSIS PLAN

9.1 Statistical Analysis Plan Summary

9.2 Statistical Analysis Plan

At our institution, patients with cT1b-2N0M0 GEA typically undergo surgery alone without additional therapy. Thus, we expect 100% of resected specimens to have evidence of cancer in historical controls. We hypothesize that neoadjuvant pembrolizumab will result in a pCR rate (Grade 1a+1b) of 15%. A sample size of 33 patients will provide 90% power with one-sided alpha 0.1 to detect this pCR rate using neoadjuvant pembrolizumab. More specifically, we will use an optimal, Simon two-stage design to test the null hypothesis that the Grade 1 response rate is 1% vs. the alternative that it is 15%. Fifteen patients will be enrolled in the first stage and if no complete pathological responses are observed the trial will be terminated for futility. If one or more responses are seen, an additional 18 patients will be studied for a total of 33. Two or more responses in 33 patients will indicate that the treatment is promising, whereas 0/15 or 1/33 will be considered a negative result. Patients who receive pembrolizumab but do not go to surgery will be counted as not having achieved a pCR.

We will also assess activity in the subset of patients who are PD-L1 positive. Assuming an approximate PD-L1 positivity incidence (CPS score ≥ 1) of 50% of all patients enrolled, this sample size of 16 expected PD-L1 positive patients will provide over 95% power with one-sided alpha 0.05 to detect a pCR rate (Grade 1a+1b) of 30% vs. 1% using neoadjuvant pembrolizumab in this preplanned subset. Using a higher CPS cutoff of ≥ 10 we assume 20% of patients will be PD-L1 positive based on recent data, and the sample size of 7 expected PD-

L1 positive patients will provide 67% power with one-sided alpha 0.05 to detect a pCR rate (Grade 1a+1b) of 30% vs. 1%

Complete responses (R0) will be tabulated along with an exact 90% confidence interval. DFS and OS will be estimated using the Kaplan-Meier method. Adverse events will be summarized by type, grade, and attribution to the study drug.

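### The "pCR rate" is the regression grade of the primary tumor with no condition on resected nodes, so a positive result cannot be called pathologic complete response as the plan stands

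*Combined protocol and SAP*

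**What the plan says.** Section 3.1 gives the pCR rate as the primary objective. The measurement rule follows: "Regression of the primary tumor will be documented by the amount of viable tumor versus the amount of fibrosis (Becker Criteria". The top category is "Grade 1a: complete remission (pCR), no residual tumor/tumor bed"; Grade 1b allows less than 10% residual tumor. The hypothesis then widens the label to both grades: "The pCR rate (Grade 1a+b response) in patients with cT1b-T2N0 GEA" is expected to be 15%.

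Section 9.2 carries this into the analysis. A Simon two-stage design will "test the null hypothesis that the Grade 1 response rate is 1% vs. the alternative that it is 15" percent. The trial stops if none of the first 15 patients responds. Otherwise 18 more are enrolled, and "Two or more responses in 33 patients will indicate that the treatment is promising"; 1 of 33 is negative.

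The nodes will be examined: section 2.1 prescribes "tumor resection with either D2 or two-field lymphadenectomy". Neither section, however, says how tumor in a resected node affects the response. The secondary objectives in 3.2 add the rates of each regression grade and R0 resection, which is defined by margins. No nodal result is listed.

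**The concern.** On the stated rule, a Grade 1 primary with viable tumor in a node is a response and enters the pCR rate. This sits badly with two of the protocol's own statements.

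- Section 4.2.1 says survival depends on the extent of disease, "in particular the depth of invasion and nodal status", and section 4.2.3.1 offers pCR as an early surrogate for survival.
- Section 9.2 builds its contrast on historical surgery-alone specimens, all of which are expected to contain cancer. A specimen with tumor in its nodes contains cancer too, and so does every Grade 1b specimen.

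The case can arise because entry requires clinical N0 (EUS, CT and PET/CT in 6.1.1) and pathological nodal status is first known at surgery, 8-11 weeks after the first dose. The count is small: one patient separates 1/33 (negative) from 2/33 (promising), and one patient decides whether the trial passes the first stage. If nodal status is considered only after the results are known, the choice of definition could rest on one or two identified patients.

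**Working it through.** **Inputs.** From 9.2: n1 = 15, stop at 0 responses; 18 more patients; positive at 2 or more of 33; null 1%, alternative 15%; one-sided alpha 0.10; power 90%. Not in the documents: q, the share of primary-tumor responders with positive nodes. I assume 10%, 20% and 30%; q = 0 reproduces the plan.

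**Step 1: reproduce the design.** The trial is negative if stage 1 has no response, or has exactly one and stage 2 has none. With response rate p,

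P(positive) = 1 − (1−p)^15 − 15p(1−p)^14 × (1−p)^18 = 1 − (1−p)^15 − 15p(1−p)^32.

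- p = 0.01: 1 − 0.8601 − 0.1087 = 0.031.
- p = 0.15: 1 − 0.0874 − 0.0124 = 0.900.

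The stated power reproduces, and exact alpha is well inside 0.10. A search over two-stage designs also confirms 0/15 then 1/33 as the optimal Simon design for these inputs.

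**Step 2: how often the two definitions disagree.** Node-negative responders are a subset of primary-tumor responders. Any trial that is positive on the node-negative count is therefore positive on the primary-only count, and the chance of different verdicts is the difference of the two probabilities: P(positive at p) − P(positive at p(1−q)). Both counts use the same two-stage rule.

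| True primary-tumor rate | q | Node-negative rate | P(positive), primary only | P(positive), node negative | Different verdicts |
|---|---|---|---|---|---|
| 15% | 10% | 13.5% | 0.900 | 0.867 | 3.3% |
| 15% | 20% | 12.0% | 0.900 | 0.823 | 7.7% |
| 15% | 30% | 10.5% | 0.900 | 0.765 | 13.5% |
| 10% | 10% | 9.0% | 0.743 | 0.691 | 5.2% |
| 10% | 20% | 8.0% | 0.743 | 0.630 | 11.2% |
| 10% | 30% | 7.0% | 0.743 | 0.560 | 18.2% |

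As q approaches 0, the last column approaches 0.

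**Step 3: how often the result sits on the boundary.** The chance of passing stage 1 and ending with exactly 2 of 33 is [C(33,2) − C(18,2)] p²(1−p)^31 = (528 − 153) p²(1−p)^31 = 375 p²(1−p)^31. This is 5.5% at p = 0.15 and 14.3% at p = 0.10.

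**Step 4: precision at the boundary.** Exact 90% intervals are 0.2-13.6% for 1/33 and 1.1-17.9% for 2/33. The verdict changes between two results whose intervals largely overlap, so the label on each responder matters.

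**The case against.** The strongest defence is that the primary-only grade was chosen for a reason. Section 4.2.3.1 reports that "complete or subtotal tumor regression has been shown to be a prognostic factor independent from ypT and ypN stage". That supports Grade 1 regression as a prognostic measure in its own right, and it stands. It does not make the grade a complete response of the disease. The same sentence does not show the converse, that ypN adds information beyond the grade; the support for nodal status comes from 4.2.1.

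It may also be said that the documents never discuss a node-positive responder, so the case is merely unspecified, and that the specimen-level sentence in 9.2 could exclude it. The documents are indeed silent on the case. But the written rule has one criterion, the grade of the primary tumor, and that sentence describes historical controls. It does not alter who counts as a responder.

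A reader might infer three stronger things that the documents do not support:

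- **That the test is invalid or its error rate inflated.** The null is stated for the Grade 1 rate, and for that quantity exact alpha is 3.1%.
- **That ypN0 must be built into the Simon endpoint.** This is a trade-off. If 15% is the primary-tumor rate, power under the unchanged rule falls from 90.0% to 86.7-76.5% for q of 10-30%, and 15% was not proposed as a node-negative rate. Nor would it repair the label, since Grade 1b with ypN0 still has viable tumor in the primary.
- **That a node-positive responder is likely to decide the trial.** Given exactly two responders, the chance that at least one is node positive is 1 − (1−q)², or 19-51%. But exactly two responders has a probability of only 5.5% at a true rate of 15% and 14.3% at 10%. The unconditional figures in the table are the fair measure.

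**Conclusion.** The concern holds as a gap in the definition and naming of the endpoint. It is not an error in the sample size or the test. As written, a positive trial shows complete or subtotal regression of the primary tumor in at least 2 of 33 patients. It does not show pathologic complete response, because neither tumor-free nodes nor a tumor-free primary is required.

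The size depends on a nodal rate that the documents do not give. With q of 10-30%, the two counts disagree in 3.3-13.5% of trials at a true primary-tumor rate of 15% and in 5.2-18.2% at 10%. Patients are staged N0 before entry, so q could be lower and the disagreement smaller. The naming problem does not depend on q, because Grade 1b is included whatever the nodes show. The change should be made before results are known; the design need not be reopened.

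**What to change.** 1. In 3.1 and 9.2, keep the Becker Grade 1 rate for the Simon decision and name it Grade 1 (complete or subtotal) primary-tumor regression. Use the same name in the stage-one stopping sentence of 9.2, which now speaks of complete responses. State explicitly that nodal status does not enter this decision.
2. In 9.2, add two prespecified results: the rate of Grade 1a with ypN0 and the rate of Grade 1 with ypN0. Give each an exact 90% interval over all dosed patients, matching the analysis set in 6.6.
3. List ypN for each responder.
4. Use "pathologic complete response" in conclusions only for Grade 1a with ypN0.

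The cost is wording and two lines of analysis. The nodes are already resected, and no procedure, visit or patient is added. N, the decision rule, alpha and power stay as they are. The downside is that the rate that may be called pCR can be lower than the Grade 1 rate. If the sponsor prefers to put ypN0 into the primary endpoint, the 15% alternative and the sample size must be re-examined first.

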3.2 Secondary Objectives & Hypotheses

Objectives:

- To determine the R0 resection rate in patients with cT1b-2N0 GEA treated with neoadjuvant pembrolizumab. Proximal, distal, and circumferential margins will be assessed to determine the completeness of resection. The absence of tumor cells at the proximal and distal margins will be required to be classified as an R0 resection.
- To determine rates of Grade 1a (complete); 1b (minimal residual disease); 2 (partial response); and 3 (no response) pathologic response grades (PRG).
- To evaluate the safety/ tolerability of pembrolizumab in patients with cT1b-2N0 GEA
- To determine the DFS measured from the time of first pembrolizumab dose
- To determine OS measured from the time of first pembrolizumab dose

Hypotheses:

- a. R0 resection rate will be greater than 95%.
- b. A subset of cases will be G1b and G2 responses.
- c. Pembrolizumab will be safe and tolerable. Patients will successfully complete neoadjuvant therapy and undergo surgery 8-11 weeks after first dose of pembrolizumab.
- d. The DFS rate will be improved compared to historical controls.
- e. OS will be improved compared to historical controls.

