3.3 Exploratory Objectives

- a. To evaluate rates of PD-L1 positive expression (by CPS score ≥ 1 and ≥ 10), MSI status, TMB and EBV status in pre-treatment biopsy specimens.
- b. To evaluate whether PD-L1 expression, MSI status, TMB and/or EBV status in pre-treatment biopsy specimen is a predictive biomarker for pCR/PRG/R0 to pembrolizumab and other clinical outcomes.
- c. To evaluate interval change in PD-L1 expression (by CPS score) pre/post pembrolizumab therapy in resected pathological specimens (if residual tumor is present).
- d. To determine the somatic genomic changes of actionable cancer related genes (mutation, amplification, indels, and translocation) using targeted deep next-generation sequencing (NGS) oncopanel in pre-treatment specimen and in resected specimen (if tumor is still present) and correlate with clinical outcomes (pCR/PRG, R0 rate, DFS, OS) and other molecular markers.
- e. To evaluate ctDNA NGS pre-pembrolizumab, post-pembrolizumab, post-surgery, and if applicable at time of recurrence, and correlate with clinical outcomes (pCR/PRG, R0 rate, DFS, OS) and molecular markers.
- f. To determine baseline and interval changes in whole-exome RNAseq expression analysis pre-/post- therapy.
- g. To evaluate fecal flora via Fecal 16S RNA seq pre-pembrolizumab, post-pembrolizumab, post-surgery, and if applicable at time of recurrence, and correlate with clinical outcomes.

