6.6 Participant Replacement Strategy

Patients that are not treated by intention to treat will be replaced to the total 33 patients intended. All patients who receive the first dose of pembrolizumab will be included in analysis per intention to treat. Patients who receive at least one dose of pembrolizumab and then do not proceed to surgery will be considered grade 3 response.

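### The only R0 criterion names the proximal and distal margins and omits the circumferential margin, although section 3.2 assesses all three for completeness of resection (minor).

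*Combined protocol and SAP*

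**What the plan says.** Section 3.2 lists the R0 resection rate as a secondary objective and describes its assessment in two adjacent sentences. The first is "Proximal, distal, and circumferential margins will be assessed to determine the completeness of resection". The second is the classification rule: "The absence of tumor cells at the proximal and distal margins will be required to be classified as an R0 resection". Hypothesis (a) in the same section is "R0 resection rate will be greater than 95" percent.

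Section 4.2.1 treats completeness and R0 as the same thing when it lists the determinants of survival: "ability to obtain a complete (R0) resection and pCR". Section 2.1 names R0 as a secondary endpoint without defining it, and notes that "Surgical approach will vary based upon tumor location".

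Section 3.3 uses R0 again as an outcome. Objective b asks whether a baseline marker "is a predictive biomarker for pCR/PRG/R0 to pembrolizumab and other clinical outcomes". Objective e plans to "correlate with clinical outcomes (pCR/PRG, R0 rate, DFS, OS) and molecular markers", and objective d makes a similar link for tumor sequencing.

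Section 9.2 plans a tabulation of R0 with an exact 90% interval and says nothing about margins. That sentence labels R0 as a complete response, not as a resection outcome. Section 6.6 states: "All patients who receive the first dose of pembrolizumab will be included in analysis per intention to treat". It assigns a response grade to treated patients who do not reach surgery, and 9.2 counts them as not having a pCR. Neither section says how they count for R0.

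**The concern.** Three margins are examined to decide whether the resection is complete, but the classification rule uses two. The circumferential result is collected and then has no stated role. A pathologist or data manager who applies the one written criterion could record R0 for a specimen with tumor at the circumferential margin. Another could read the two sentences together and record the same specimen as not R0. Section 11 describes participating institutions beyond the lead center, so both readings could occur within one trial.

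What is at stake is the value reported for one secondary endpoint against its 95% hypothesis, and the R0 grouping in three exploratory objectives. If the definition is settled only after the circumferential results are known, the choice could also be influenced by them.

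**Working it through.** **Inputs.** N = 33, and the design of 15 then 18 patients with at least 2 responses for success, 1% against 15% (9.2). R0 hypothesis above 95% and the margin rule (3.2). Exact 90% interval for R0 (9.2).

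**1. The plan's own design figure.** The only stated figure with a derivation belongs to the primary endpoint. The probability of success is 1 − P(X1 = 0) − P(X1 = 1) × P(X2 = 0), with X1 from 15 patients and X2 from 18.
- At 15%: 1 − 0.85^15 − (15 × 0.15 × 0.85^14) × 0.85^18 = 0.900, which matches the stated 90% power.
- At 1%: the same formula gives 0.031, within the one-sided 0.1 limit.

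R0 does not enter this calculation, so changing the R0 rule changes neither N nor the decision rule. The 95% R0 figure is a hypothesis with no derivation to reproduce.

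**2. Direction.** Every specimen clear at all three margins is also clear at two. The set classified R0 under three margins is therefore contained in the set classified R0 under two, and the two-margin rate is equal or higher.

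**3. What above 95% means with 33 resections.** 0.95 × 33 = 31.35, so at least 32 must be R0. Each specimen is worth 1/33 = 3.0 points.

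**4. Exact 90% intervals (Clopper-Pearson).** The lower limit is the 5th percentile of Beta(x, 33 − x + 1) and the upper limit is the 95th percentile of Beta(x + 1, 33 − x).

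| R0 count | Rate | Exact 90% CI |
|---|---|---|
| 33/33 | 100% | 91.3 to 100% |
| 32/33 | 97.0% | 86.4 to 99.8% |
| 31/33 | 93.9% | 82.1 to 98.9% |

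Moving one specimen from 32/33 to 31/33 takes the observed rate below 95%. All three intervals contain 95%.

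**5. Exploratory groups.** If the observed rate is above 95%, at most 1 of 33 patients is non-R0. One reclassified specimen changes that group from 0 to 1 or from 1 to 2.

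**6. How often it might happen (assumption only).** The documents give no rate of specimens positive at the circumferential margin alone. If that rate is c, the chance of at least one among 33 is 1 − (1 − c)^33, and the average overstatement is 100c points.
- c = 1%: 28% chance, 1.0 point.
- c = 3%: 63% chance, 3.0 points.
- c = 5%: 82% chance, 5.0 points.

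Nothing in the documents supports any of these values over a smaller one.

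**The case against.** The strongest reply is grammatical. The rule says clear proximal and distal margins are required. That is a necessary condition, not a sufficient one. Read with the sentence before it, and with 4.2.1 equating complete with R0, a circumferential-positive specimen might properly be called incomplete. This is fair: a reader might infer that the protocol declares such specimens to be R0, and it does not. But if the sentence is only a necessary condition, R0 has no complete definition anywhere, and the same edit is needed.

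A second reply is that two margins may be deliberate, because the trial covers esophageal and gastric tumors, the operation varies by site, and some specimens may have no circumferential margin. The documents do not give this reason, but they do not rule it out. The fix allows for it.

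A third reply is that little follows from the change. No test or decision attaches to R0, and a comparison group of 0, 1 or 2 patients is uninformative under either rule. This stands, and it sets the severity.

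Finally, the denominator may matter more than the margin. If all 33 treated patients form the denominator and two are not resected, R0 cannot exceed 31/33 under either margin rule. This also stands. It is a separate gap, to be put to the sponsor as a question.

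**Conclusion.** The point holds as a minor one. The only R0 criterion leaves out a margin that the same section assesses for completeness. Applied as written, it permits a circumferential-positive specimen to be counted as R0, and any resulting bias is upward. One such specimen can move the observed rate from 97.0% to 93.9%, across the protocol's own hypothesis. That statement assumes 33 resections and 32 counted as R0 under the two-margin rule.

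Two stronger readings are tempting. A reader might infer that the R0 rate will be materially inflated; the documents give no circumferential-positivity rate, and the effect may be small in cT1b-T2 disease. A reader might also infer that crossing 95% changes a trial conclusion; R0 is descriptive, the intervals on both sides contain 95%, and the pCR rule of 2 or more in 33 does not use it.

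**What to change.** In 3.2, replace the rule with wording to this effect: a resection is R0 only if no tumor cells are found at any margin assessed, meaning proximal, distal and, where the specimen has one, circumferential. If the two-margin rule is intended, say so and report the number of circumferential-positive specimens beside the R0 rate. Settle this before resection results are reviewed.

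Ask the sponsor two questions on 9.2, without presuming the answers: does the sentence that labels R0 as a complete response refer to resections or to pathologic responses, and is the R0 denominator all treated patients or only those resected?

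The cost is a wording change. The circumferential margin is already assessed, so no new procedure is needed. The downside is a possibly slightly lower R0 rate.
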